4.3 Secondary Endpoints

- Technical Success: All A0 and A1 ablation classification determinations (complete tumor ablation with a surrounding minimal margin) as assessed by cone beam CT imaging, immediately following the ablation procedure.
- Navigational Success: Successful navigation to the targeted peripheral lung tumor(s) as confirmed using cone beam CT (CBCT).
- Local Tumor Progression (LTP): Recurrence of originally ablated target tumor(s) within or abutting the ablation zone using 30-day post-ablation imaging as the baseline. Measuring progression details will be outlined in a separate Imaging Charter.
- Local Tumor Progression Free Survival (LTPFS): Time from the ablation until local tumor(s) progression (LTP) or death, whichever occurs first. Measuring progression details will be outlined in a separate Imaging Charter.

- Progression Free Survival: Time from the original ablation until tumor(s) progression or death, whichever occurs first (includes local, regional, or distant progression). Measuring progression details will be outlined in a separate Imaging Charter.
- Disease (cancer) Specific Survival: Time from the original ablation until death from the treated primary malignancy.
- Overall Survival: Time from the original ablation until subject death (includes death from any cause).
- Repeat Ablation Efficacy Rate: Rate of original tumors that have been re-ablated successfully (i.e., Technical Success of tumors that have been re-ablated/all original tumors that have been re-ablated).
- Change in all available PFTs (pulmonary function tests) from pre-ablation baseline values to values at 3 months, 6 months, and 12 months post-ablation.
- Change in overall health-related quality of life (HRQOL) and sub-scales, including physical functioning and pain domains, per the validated EORTC QLQ-C30 and QLQ-LC13 questionnaires throughout the duration of the study.

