5.5 Prior and Concomitant Therapy

Subjects may continue with their current medical care throughout the duration of the study, including medications, except as noted in the Exclusion Criteria section of this protocol. All relevant concomitant medications taken within 30 days of Visit 2 and all relevant concomitant medications taken throughout the study, including but not limited to antiplatelet, anticoagulants, chemotherapy, immunotherapies, steroids, anti-inflammatories, NSAIDs, opioids, antibiotics, and medications used to treat adverse events will be recorded on the relevant eCRF page. Components of the anesthesia medication used for the ablation procedure do not need to be recorded on the eCRF page.

In order to avoid confounding the safety and primary effectiveness evaluation, specific treatments/therapies are restricted prior to and after the ablation procedure for given timepoints. The following table summarizes the treatments/therapies restriction timepoints:

Type of Treatment/Therapy	Restriction Prior to Ablation Procedure	Permitted Post Ablation Procedure	Note
Antiplatelet agents (e.g., aspirin, clopidogrel, prasugrel, ticagrelor)	5 days	48-72 hours	Exclusion Criterion #9
Warfarin	3-5 days, or until INR < 1.5	48-72 hours	Exclusion Criterion #10
Anticoagulants (e.g., rivaroxaban, apixaban, dabigatran, edoxaban)		48-72 hours	Exclusion Criterion #11
Lung ablation, surgical resection, radiotherapy, or other treatment procedure	30 days	30 days (or until Primary Endpoint assessed)	Exclusion Criterion #18
Systemic therapy such as chemotherapy, targeted drug therapy (e.g., tyrosine kinase inhibitors), or immunotherapy (e.g., PD-1 antagonists or CTLA inhibitors)	14 days	30 days (or until Primary Endpoint assessed)	Exclusion Criterion #19

After the restriction timepoint, the above-referenced treatments/therapies may be used at the discretion of the PI and treating oncologist, and should be noted in the eCRFs.

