If target tumors recur after the original ablation, they may be re-ablated after the Visit 3 assessment for Technique Efficacy has been completed. A re-ablation will not change or extend the follow-up schedule. Additionally, no single tumor should be ablated more than twice during the 12-month follow-up period (i.e., the original ablation procedure and a re-ablation procedure at a separate visit). **Robotic Navigation Portion of Procedure**

Cone beam CT will be used in all cases to confirm the presence of the tumor(s) immediately before initiating the procedure. Navigation to the target tumor(s) will be performed using the MONARCH Platform. The MONARCH Platform is a novel robotic-assisted, software driven, endoscope articulation system which can electromechanically insert, steer, and withdraw a flexible endoscope to patient airways under continuous, real-time, direct, visual control by a physician operator.

Users must follow all instructions for use supplied with the MONARCH Platform, its components, instruments, and accessories, including any instructions for use (IFUs) provided with instruments or accessories. The provided IFU is the primary source for detailed safety information. The MONARCH Platform and its accessories are intended to provide bronchoscopic visualization of and access to patient airways for diagnostic and therapeutic procedures.

Microwave Ablation Portion of Procedure

The ablation will be performed using the NEUWAVE FLEX MC Microwave Ablation System, per the device's User Manual and Instructions for Use (IFU), and the performing physician's clinical judgment.

All ablations will be performed under general anesthesia via a transbronchial approach. Prophylactic antibiotics should be administered pre-ablation per site SOC.

The size of the tumor(s) will be measured and recorded on the day of ablation (Visit 2). Afterwards, the Monarch Platform will be used to navigate the microwave ablation probe to the target tumor and CBCT will be used to confirm probe position/placement.

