**Time to Event Endpoints:**

Local Tumor Progression Free Survival (LTPFS) is defined as: Time from the ablation until local tumor(s) progression (LTP) or death, whichever occurs first.

Progression Free Survival (PFS) is defined as: Time from the original ablation until tumor(s) progression or death, whichever occurs first (includes local, regional, or distant progression). Specifically: For local tumors, time from the original ablation until tumor(s) progression or death, whichever occurs first. For regional and distant tumors, time from study day 0 or last local therapy (if treated after study initiation) until tumor(s) progression or death, whichever occurs first.

Disease (cancer) Specific Survival (DSS) is defined as: Time from the original ablation until death from the treated primary malignancy.

Overall Survival (OS) is defined as: Time from the original ablation until subject death (includes death from any cause).

Local Tumor Progression Free Survival (LTPFS), Progression Free Survival (PFS), Disease Specific Survival (DSS), and Overall Survival (OS) will be estimated using the Kaplan-Meier method with 95% confidence intervals provided at month 12. The time from the day of the initiation ablation procedure to the specific event will be derived.

Patients who are re-ablated are considered as reaching an event respectively for each of the LTP, LTPFS and PFS event definitions.

Patients without a progression event, as defined above, will be censored by the last contact date (the last date in the study).

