## 8.10 Central Review v. Investigator on Effectiveness Analysis

The effectiveness-based endpoints will be evaluated both by the treating physician (i.e., PI) as well as the independent Central Review Committee. Both sets of results will be summarized in the final report, with the Central Review Committee results being specified as the primary result for Technique Efficacy, Technical Success, Local Tumor Progression, Other Progression (regional and distant), the smallest/largest ablation zone, and the smallest margin.

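### SAP 8.8.2 makes re-ablation of a target tumor an LTP, LTPFS and PFS event but has no rule for radiotherapy or resection of the same tumor, so a local failure can be classified by the salvage chosen

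*SAP*

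**What the plan says.** **Event rule.** SAP 8.8.2, under Time to Event Endpoints: "Patients who are re-ablated are considered as reaching an event respectively for each of the LTP, LTPFS and PFS event definitions". No sentence in the SAP does the same for radiotherapy, resection or any other local treatment of a target tumor.

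**Censoring rule.** Same section: "Patients without a progression event, as defined above, will be censored by the last contact date (the last date in the study". SAP 8.13 adds only that standard censoring assumptions apply.

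**Definitions.** LTP (Protocol 4.3, repeated in SAP 8.8.2) is "Recurrence of originally ablated target tumor(s) within or abutting the ablation zone using 30-day post-ablation imaging as the baseline". Local tumor progression free survival (LTPFS) is "Time from the ablation until local tumor(s) progression (LTP) or death, whichever occurs first". Progression free survival (PFS) adds regional and distant progression. For those tumors, local therapy on study restarts the clock and is not an event: "For regional and distant tumors, time from study day 0 or last local therapy (if treated after study initiation) until tumor(s) progression or death".

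**Permitted treatment.** Protocol 5.5 restricts lung ablation, resection, radiotherapy and other treatment procedures for 30 days or until the primary endpoint has been assessed. Then: "After the restriction timepoint, the above-referenced treatments/therapies may be used at the discretion of the PI and treating oncologist". On re-ablation, Protocol 6.1 says: "If target tumors recur after the original ablation, they may be re-ablated after the Visit 3 assessment for Technique Efficacy has been completed".

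**Who reads what, and when.** SAP 8.10 gives central review precedence, "with the Central Review Committee results being specified as the primary result for Technique Efficacy, Technical Success, Local Tumor Progression". The central assessment grid (Protocol 4.5, SAP section 1) has Technique Efficacy at Visit 3 and progression at Visits 4, 5 and 6 only.

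**The concern.** The SAP lets one salvage treatment stand in for an imaging event and is silent on the others. Protocol 3.0 itself presents surgery, stereotactic radiotherapy and ablation as accepted alternatives in this population, so use of the others after Visit 3 is foreseeable.

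The clearest case is residual tumor on the Visit 3 scan. That scan is the LTP baseline, so disease already visible on it is not plainly a recurrence, and no progression read is scheduled until Visit 4. If the site re-ablates in the interval, the subject has an LTP, LTPFS and PFS event. If the site irradiates or resects the same tumor, no rule creates an event, and unless something is read later the subject stays at risk, event-free, to last contact. Two further routes lead to the same gap: treatment between scheduled scans, and treatment on a site reading that central review does not share.

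At stake is the interpretation of the trial's local-control results, which could vary between sites with the salvage they tend to use. LTPFS and PFS are also two of the four endpoints that SAP section 5 singles out for 12-month confidence intervals if the primary endpoint succeeds. Elsewhere the SAP does recognise the issue: 8.8.2 and 8.9 allow separate lung-function, quality-of-life and ECOG summaries that exclude patients who had re-ablation or other treatment.

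**Working it through.** **1. The plan's own figure.** The only design calculation is for the primary endpoint (SAP section 7): performance goal p0 = 0.80, expected rate p1 = 0.90, one-sided alpha 0.025, power above 90%.

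n = [(1.960 × √(0.80 × 0.20) + 1.282 × √(0.90 × 0.10)) / 0.10]² = 136.5, rounded up to 137. Power at 137 is 90.1%, and 137/0.95 gives 145. The plan's figures reproduce. None depends on this point. No expected rate or event count is stated for LTP, LTPFS or PFS.

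**2. The interval without a scheduled progression read.** Visit 3 is day 30 (−7 to +14), so days 23 to 44. Visit 4 is 3 months ± 2 weeks; taking 3 months as 91 days, days 77 to 105. The gap is 77 − 44 = 33 days at the shortest and 105 − 23 = 82 days at the longest, roughly 5 to 12 weeks.

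**3. The same failure under the SAP as written.**

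| What happens to the target tumor | LTP / LTPFS / PFS result |
|---|---|
| Central LTP read first, then any treatment | Event, whatever the treatment |
| Residual tumor at Visit 3, re-ablated before Visit 4 | Event |
| Residual tumor at Visit 3, irradiated or resected before Visit 4 | No event from any stated rule |
| Re-ablated on the site's reading, no central LTP | Event |
| Irradiated or resected on the site's reading, no central LTP | No event from any stated rule |

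For PFS, regional or distant progression may still supply an event in the no-event rows; death may do so for LTPFS and PFS.

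**4. Ceiling for the Visit 3 route.** Inputs: Technique Efficacy 0.90, 137 evaluable subjects and one target tumor per subject (all SAP section 7). Subjects with residual tumor: 0.10 × 137 = 13.7, about 14. If a share g of them is treated by something other than re-ablation, and every one is salvaged before Visit 4 with no other event, the contribution to LTP is 10 × (1 − g) points: 10 at g = 0, 5 at g = 0.5, 0 at g = 1. The swing is at most about 10 points.

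**5. General size.** Overstatement of 12-month local control = f × s × q, where f is the true local failure rate, s the share of failures salvaged other than by re-ablation, and q the share of those with no centrally read LTP. All three are assumptions. The value f = 15% is scaled to the local control above 85% quoted for percutaneous ablation in Protocol 3.0. With s = 50%:

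| f | q = 0 | q = 25% | q = 50% | q = 100% |
|---|---|---|---|---|
| 10% | 0 | 1.25 points | 2.5 points | 5.0 points |
| 15% | 0 | 1.9 points | 3.75 points | 7.5 points |

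One unrecorded salvage shifts the estimate by about 1/145 = 0.69 points (1/137 = 0.73).

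**6. Missing event or censoring date?** A Kaplan-Meier simulation (145 subjects, 10% random dropout, failures at 3, 6 or 12 months, f = 15%, s = q = 50%) gave 88.6% with last-contact censoring, 88.5% with censoring at salvage, and 85.0% with salvage counted as an event. The missing event drives the difference; the censoring date hardly matters.

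**The case against.** A reader might infer that patients salvaged by radiotherapy or surgery never count as local failures, and that local control is therefore overstated. The documents do not support that. LTP is an imaging finding with central review primary, so a recurrence read centrally and then irradiated or resected is already an event for all three endpoints. The committee also reviews all CT scans taken in the study. This objection stands, and it makes the bias conditional.

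The direction is not fixed either. A site-chosen re-ablation is an event even without a central LTP, which works against the device. If residual tumor on the baseline scan is not LTP in the first place, counting it when re-ablated adds events beyond the imaging definition. This also stands. It strengthens the case for a single rule, because under either view the classification still depends on modality.

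Residual tumor at Visit 3 is already a failure of the primary endpoint, so it is not hidden from the trial's results. Nor does later treatment make a subsequent LTP impossible: chest CT continues at Visits 4 to 6. Both points are correct and limit the consequence.

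Finally, Protocol 4.3 leaves progression details to an Imaging Charter that is not among the documents. The Charter may settle how residual disease is read. It does not remove the inconsistency, because the rule turning a treatment into an event sits in the SAP and names only one treatment.

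**Conclusion.** The inconsistency is real and follows from stated rules. When a target tumor is treated without a prior centrally read LTP, SAP 8.8.2 classifies the failure by salvage modality, and local control can be overstated.

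The size cannot be derived, because the documents give no salvage rates, modality split or timing. It is zero if central LTP always comes first. About 10 points should not be read as an estimate: it is the ceiling for the Visit 3 route, resting on 0.90 Technique Efficacy, salvage of every failure before Visit 4 and no other event. The assumed cases at s = 50% run from 0 to 7.5 points.

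The endpoints affected are secondary and carry no hypothesis test. The primary endpoint and the sample size of 145 do not change. The point merits an SAP amendment before database lock.

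**What to change.** Replace the re-ablation sentence in SAP 8.8.2 with one treatment-neutral rule, for example:

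> Any local treatment directed at a target tumor or its ablation zone for residual or recurrent disease (re-ablation, radiotherapy, resection or other) is an event for LTP, LTPFS and PFS, dated at the earlier of the treatment and a centrally read LTP. If the zone is removed or irradiated for another reason, local follow-up is censored at that date.

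Add:

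- A sensitivity analysis counting only centrally read LTP as local failure for every modality, including re-ablation, with censoring at other local treatment of the zone. With the main rule, this shows how far treatment decisions drive the result.
- A supportive LTP summary restricted to target tumors that achieved Technique Efficacy at Visit 3, so that residual tumor and later recurrence are not mixed.
- A table of salvage by modality and by whether central LTP came first.

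This changes how treatment is counted, not which treatment is given.

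The cost is SAP wording and one derivation. Concomitant procedures are already collected from screening onward, and SAP 8.6 lists disease progression as an indication. The documents do not show a link from a procedure to a specific target tumor, or a category for residual disease, so some tumor-level linkage is needed. The LTP, LTPFS and PFS figures may look slightly less favourable.

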### **Other Secondary Endpoints:**

Navigational Success is defined as: Successful navigation to the targeted peripheral lung tumor(s) as confirmed using CBCT.

Repeat Ablation Efficacy Rate is defined as: Rate of original tumors that have been re-ablated successfully (i.e., Technical Success of tumors that have been re-ablated/all original tumors that have been re-ablated).

Change in all available pulmonary function tests (PFTs) is defined as from pre-ablation baseline values to values at 3 months, 6 months, and 12 months post-ablation.

Change in overall health-related quality of life (HRQOL) and subscales, including physical functioning and pain domains, per the validated EORTC QLQ-C30 and QLQ-LC13 questionnaires throughout the duration of the study.

Categorical variables will be summarized with counts and percentages. These include Navigational Success, and Repeat Ablation Efficacy.

Change in all available PFTs (pulmonary function tests) from pre-ablation baseline values to values at 3 months, 6 months, and 12 months post-ablation, change in overall health-related quality of life (HRQOL) and subscales (including physical functioning and pain domains) per the validated EORTC QLQ-C30 and QLQ-LC13 questionnaires throughout the duration of the study will be summarized descriptively with n, mean, SD, min, max, Q1, and Q3.

Re-ablation or subsequent treatment may impact the quality of life and/or pulmonary function. Hence, a separate summary may be presented for PFT, HRQOL by excluding those patients who have re-ablation, or received other treatment during the study.

### **8.9 Exploratory Endpoints**

Level of Procedure Related Pain: Subject reported outcome determined by the Numeric Pain Scale.

Subject functionality as measured by distribution of Eastern Cooperative Oncology Group (ECOG) classification scores over time.

Hospital Readmission Rate: Any unplanned admission or readmission to the hospital within 30 days of the ablation procedure due to an adverse event.

Procedural cost (UB-04) for US sites.

Number of systemic chemotherapy-free days from time of ablation through the duration of the study.

Number of systemic chemotherapy-free days will be summarized separately for those subjects without any plans for systemic therapy post local therapy and for subjects with plans for post ablation/SBRT/surgery systemic therapy.

Categorical variables will be summarized with counts and percentages. These include hospital readmission (unplanned admission or readmission within 30 days of ablation due to an AE) and ECOG. Re-ablation or subsequent treatment may impact the ECOG results. Hence, a separate summary may be presented for ECOG excluding those patients who have re-ablation, or received other treatment during the study.

Level of Procedure Related Pain (0 to 10), procedural cost from UB-04 form, if available, and number of systemic chemotherapy-free days (from time of ablation through the duration of the study) will be summarized descriptively with n, mean, SD, min, max, Q1, and Q3.

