7.6 Visit 6 – 12-month Follow-up

Visit 6 occurs 12 months (\pm 1 month) after the first ablation procedure. The subject will visit the study site for the following assessments:

- Document any changes or updates to the subject's relevant concomitant medications (blood thinning/anticoagulants, antiplatelets, opioids, systemic chemotherapy, systemic steroids, immunotherapies, anti-inflammatories, NSAIDs, antibiotics, and medications used to treat adverse events)
- Document any changes or updates to the subject's concomitant procedures.
- Complete two validated quality of life questionnaires: EORTC QLQ-C30 and the lung-specific QLQ-LC13. These questionnaires should be administered in person, during the study visit. However, they may be administered over the phone, when needed.
- Collect key vitals: blood pressure, heart rate, and pulse oximetry.
- Evaluate ECOG performance status.

- Obtain PFTs, which include Spirometry (e.g., FEV1, FVC, FEV1/FVC, FEF25-75, Peak Expiratory Flow, and Maximum Ventilation Volume), Diffusion Capacity (DLCO), Total Lung Capacity (TLC), Functional Residual Capacity (FRC), and Residual Volume (RV).
- Complete chest CT, abdomen and pelvis CT, brain MRI (if site SOC), and extremity CT or MRI (if site SOC) to determine Tumor Progression. Contrast-enhanced images are preferred but not required. If a site takes a PET scan per SOC, the other images should also be taken, per protocol:
 - Local Tumor Progression (LTP), defined as recurrence of the originally ablated tumor(s) within or abutting the ablation zone using Chest CT and the 30-day post-ablation imaging as the baseline.
 - Regional Tumor Progression includes new or progression of pre-existing tumors that were not previously ablated within either lung using chest CT.
 - Distant Tumor Progression includes new or progression of pre-existing tumors outside of the lung using abdomen and pelvis CT, brain MRI, and extremity CT or MRI.
- Record any applicable AEs or SAEs:
 - Record any AEs or SAEs that may have occurred within 30 days of an ablation or re-ablation procedure.
 - Record only device- or procedure-related AEs or any SAEs that may have occurred after 30 days of an ablation or re-ablation procedure.

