## 1 Study Design

This is a prospective, multicenter, single-arm study of transbronchial microwave ablation using robotic-assisted bronchoscopy in adult subjects with oligometastatic tumors ( $\leq 2\text{cm}$ ) in the lung, located in the outer two-thirds and not closer than 1cm to the pleura (including fissures), with colorectal, renal, or sarcoma histology.

Subjects with at least one oligometastatic tumor in the lung who meet all inclusion/exclusion criteria will have transbronchial microwave ablation performed using CBCT scan for probe guidance and confirmation. Subjects will be followed for 12 months following the first ablation procedure for safety and effectiveness outcomes.

Overall, the study will include up to 145 subjects across approximately 15 sites, where principal investigators will be licensed pulmonologists/interventional pulmonologists or thoracic surgeons who have completed at least 20 diagnostic cases using the MONARCH Platform including at least 5 cases using CBCT and completed the Sponsor-required FLEX MC training.

In this study, “target” tumors are defined as lung tumors that are treated with FLEX MC at the index ablation procedure (i.e., Visit 2). A subject may have a maximum of two target tumors. “Non-target” tumors are defined as lung tumors that are treated with FLEX MC during study follow-up after completion of the primary endpoint, Technique Efficacy assessments at Visit 3 (i.e., Visits 3-6). A subject may not have more than three total tumors treated with FLEX MC (including target and non-target tumors).

A central review committee of radiologists will independently review all CT scans (and other scans, as applicable) taken throughout the clinical study in an effort to standardize scan assessment and to minimize potential bias of the treating physician. Both the clinical site’s radiographic assessment and the central review committee’s assessment will be captured within the CRFs and reported within the final Clinical Study Report. The central review committee assessment for the following key endpoints will be used for the final analysis.

Assessment	Visit 1 (Screening)	Visit 2 (Ablation Visit)	Visit 3 (30 days post-ablation)	Visit 4 (3 months post-ablation)	Visit 5 (6 months post-ablation)	Visit 6 (12 months post-ablation)
Tumor size* (smallest and largest diameters)	X					
Ablation zone (smallest and largest diameters)		X				
Smallest minimal ablation margin		X				
Technical Success		X				

Technique Efficacy			X			

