### **8.13 Handling of Missing Data**

No imputation will be used for missing data or early dropouts in all analysis except in the sensitivity analyses for the primary endpoint (see Section 8.8.1). Time-to-event analyses will use standard censoring assumptions for the handling of subjects who do not have event or do not complete follow-up visits (see Section 8.8.2).

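### Systemic chemotherapy-free days are summarised as a plain count with no horizon, observed-time denominator or rule for death and withdrawal, so chemotherapy use cannot be separated from length of follow-up

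*SAP*

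**What the plan says.** SAP 8.9 defines the endpoint as "Number of systemic chemotherapy-free days from time of ablation through the duration of the study", and Protocol 4.4 defines it in the same way. The analysis is equally simple: "number of systemic chemotherapy-free days (from time of ablation through the duration of the study) will be summarized descriptively with n, mean, SD", plus extremes and quartiles. The one refinement is a split by treatment intent: "Number of systemic chemotherapy-free days will be summarized separately for those subjects without any plans for systemic therapy post local therapy", with a second summary for subjects who do have such plans.

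On follow-up, SAP 1 states: "Subjects will be followed for 12 months following the first ablation procedure for safety and effectiveness outcomes". Protocol 7.6 and the schedule of assessments let Visit 6 fall one month either side of month 12. Protocol 5.7 lists withdrawal of consent, death and loss to follow-up among the reasons for ending participation early.

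On incomplete follow-up, SAP 8.13 says "No imputation will be used for missing data or early dropouts in all analysis except in the sensitivity analyses for the primary endpoint". It adds: "Time-to-event analyses will use standard censoring assumptions for the handling of subjects who do not have event or do not complete follow-up visits". The time-to-event endpoints in SAP 8.8.2 are local tumor progression free survival, progression free survival, disease specific survival and overall survival. Chemotherapy-free days are not among them. Protocol 10.9 promises only descriptive statistics for the additional endpoints.

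**The concern.** A mean of days can be read as chemotherapy avoidance only if every subject had the same number of days available, or if a stated rule covers those who did not. Neither condition is met. A low mean could reflect heavy chemotherapy use, early deaths or early withdrawals, and the planned summary does not show which.

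The split by planned systemic therapy does not solve this. It separates subjects by intent, not by follow-up. If death or dropout differs between the two strata, their means will differ for that reason as well.

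What is at stake is modest. Protocol 3.0 gives avoiding systemic chemotherapy and its toxicity as one reason for local therapy, and mentions it again as a patient preference. This endpoint is the one that puts that idea into days, so its summary should be interpretable.

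**Working it through.** **Plan's own figure.** There is none to reproduce. The documents give no expected number of chemotherapy-free days and no 12-month death, dropout or chemotherapy rate for this trial. The 5% dropout in SAP 7 refers to the 30-day primary endpoint.

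**1. Visit window** (Protocol 7.6; 30.44 days per month).
- 11 × 30.44 = 335 days; 13 × 30.44 = 396 days; difference 61 days.
- Two completers who never receive chemotherapy can therefore differ by up to 61 days.
- A completer at month 13 with 60 chemotherapy days scores 396 − 60 = 336. A completer at month 11 with none scores 335.

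**2. Early exit, two hypothetical subjects**, with counting stopped at exit.
- Exit on day 90, no chemotherapy: count 90; share of observed days 90/90 = 100%.
- Followed 365 days, 120 of them on chemotherapy: count 365 − 120 = 245; share 245/365 = 67%.
- The count and the share rank these two subjects in opposite orders.

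**3. Early exit, effect on the mean.** Assume a constant exit rate (death or dropout), probability q of exit by day 365, and a share f of observed time on chemotherapy. Mean observed days are m = 365 × q / (−ln(1 − q)), and the mean count is m × (1 − f).

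| q (assumed) | m, which is the mean count at f = 0 | mean count at f = 20% |
|---|---|---|
| 0% | 365 | 292 |
| 5% | 356 | 285 |
| 10% | 346 | 277 |
| 20% | 327 | 262 |
| 30% | 307 | 246 |

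Down each column chemotherapy use per observed day is constant, yet the mean falls by 58 days (f = 0) or 46 days (f = 20%).

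**4. Is that range plausible?** Protocol 3.0 quotes 3-year overall survival of about 45% to 65% after image-guided ablation or SBRT. With a constant hazard, 12-month mortality is 1 − S^(1/3).
- S = 0.65 gives 13.4% and m = 340 days.
- S = 0.45 gives 23.4% and m = 320 days.

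Death alone would take 365 − 340 = 25 to 365 − 320 = 45 days off the mean for subjects who never receive chemotherapy. This lies inside the assumed range.

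**5. Two groups side by side.**
- 10% of time on chemotherapy with 30% exit: 307.0 × 0.90 = 276 days.
- 20% of time on chemotherapy with 5% exit: 355.8 × 0.80 = 285 days.

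The group with less chemotherapy has the lower mean.

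**6. The counting rule itself.** Take a subject who dies on day 100 without chemotherapy. The score is 100 if counting stops at death, and 365 if later days are counted as chemotherapy-free up to a one-year horizon. The subject drops out of the summary altogether if only completers are used. SAP 8.9 does not say which applies. Stopping at exit is the natural reading, and steps 2 to 5 use it.

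**The case against.** The endpoint is the last on the exploratory list of a single-arm study, with no test and no formal between-group comparison, so the rankings in the working are illustrations and not planned analyses. The Visit 6 window is symmetric and would mainly add spread; no systematic shift in the mean is shown from it. The exit rates and chemotherapy shares are assumed. Readers will also see related tables: medications of interest (SAP 8.6), discontinuations with reasons (SAP 8.2), and overall and disease specific survival (SAP 8.8.2). Finally, scoring an early death low can be defended as days alive and free of chemotherapy over a fixed horizon.

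Most of this stands and limits the weight of the point. It does not remove it. The neighbouring tables do not adjust the mean, and days alive and free of chemotherapy would need the fixed horizon and stated death rule that the plan lacks.

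Three stronger readings are tempting but not supported:
- A reader might infer that SAP 8.13 forbids any correction. It bars imputation and applies censoring only to time-to-event analyses. Truncating the count, dividing by observed days or estimating a cumulative incidence is not imputation.
- A reader might infer that the plan fails to measure a main benefit of the treatment. Protocol 3.0 puts a prolonged disease-free state first and adds chemotherapy avoidance as a further possibility. The Benefits text in Protocol 11.0 does not mention chemotherapy.
- A reader might infer that the plan definitely counts to each subject's own exit. The text leaves the end point of the count undefined.

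**Conclusion.** The point holds as a low-cost improvement to an exploratory endpoint. As written, the summary mixes chemotherapy use with length of follow-up, and the plan provides no adjustment, although nothing in it prevents one.

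Two completers without chemotherapy can differ by up to 61 days through the visit window alone; this rests only on the documents. The effect of early exit on the mean depends on assumptions: counting that stops at exit, a constant exit rate, and 0% to 30% exit by 12 months. Under these, the mean for subjects who never receive chemotherapy ranges from 365 to 307 days. The Protocol's own survival figures suggest a loss of about 25 to 45 days from death alone. The primary test, the sample size of 145 and the secondary endpoints are unaffected.

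**What to change.** In SAP 8.9:

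1. Cut the count at day 365. This removes the excess from late final visits (up to 396 − 365 = 31 days). It leaves a shortfall of up to 365 − 335 = 30 days for early ones, which items 3 and 4 address.
2. State how days after death and days after withdrawal are counted.
3. Report observed follow-up time next to the count. As a supportive figure, add the share of days alive and observed that were chemotherapy-free.
4. Add a 12-month cumulative incidence of first systemic chemotherapy, with death as a competing event and dropout censored, within the planned and not-planned strata already specified. The share is not enough alone, because an early death without chemotherapy scores 100%. The censoring assumes that dropout is unrelated to the chance of starting chemotherapy.
5. Use one definition of systemic chemotherapy throughout, and say whether targeted therapies and immunotherapies count; SAP 8.6 lists them separately from chemotherapies. Any version of the endpoint also needs a rule for which days of a treatment cycle are chemotherapy days.

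The cost is one derived variable, one short table and one competing-risk estimate. The dates required are those that the existing count already needs. Protocol 5.5 and the notes to the schedule of assessments require chemotherapy to be recorded but do not mention start and stop dates, so the sponsor should confirm that both are captured.
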